5.7 SAFETY ANALYSES

Descriptive statistics will be used to analyze all safety data in the SE population, unless otherwise specified. All analyses will be summarized by previous randomization and overall, unless otherwise specified.

5.7.1 Exposure to Study Drug

Exposure to study drug information will be descriptively summarized by previous randomization and overall as follows:

- Treatment duration (in weeks and years)
- Total number of administrations
- Total cumulative dose (mg)
- Duration on 225mg /300mg / 450mg/ 600mg / 900mg / 1200mg gantenerumab dosing steps (in days)
- Number of administrations on 225mg /300mg / 450mg/ 600mg / 900mg / 1200mg gantenerumab dosing steps
- Total cumulative dose on 225mg /300mg / 450mg/ 600mg / 900mg / 1200mg gantenerumab dosing steps (mg).

5.7.2 Adverse Events

AEs will be coded using the Medical Dictionary for Regulatory Activities (MedDRA) version that is current at the time of the analysis (MedDRA Version 24.0). For each group, the frequency of each AE preferred term (PT) will be defined as the number of patients experiencing at least one occurrence of the event. Each summary table will present the overall number of patients experiencing at least one AE and the total number of reported AEs. Furthermore, the AEs will be sorted by system organ class (SOC) in decreasing order of overall incidence, then by PT in decreasing order of overall incidence. Patient listings will contain PTs and comments for each AE.

The following safety information during the treatment period in the OLE (from the start of OLE until 4 weeks after the last dose in the OLE) will be summarized and listed by previous randomization and overall:

- AEs
- SAEs
- Study drug-related AEs
- Study drug-related SAEs
- AEs leading to discontinuation of study treatment
- AEs leading to dose reduction
- AEs leading to dose interruption
- AEs of special interest (AESIs)

The following safety information will be summarized and listed by previous randomization and overall separately:

- AEs starting at or after the first dose of treatment in the DB part but before 4 weeks after the last dose in the OLE
- AEs starting at or after the first dose of treatment in the DB part and unresolved before the first dose of study treatment in the OLE
- SAEs starting at or after the first dose of treatment in the DB part but before 4 weeks after the last dose in the OLE
- SAEs starting at or after the first dose of treatment in the DB part and unresolved before the first dose of study treatment in the OLE

AEs during the follow-up period (from 4 weeks after the last dose in the OLE until the CCOD) will be summarized and listed by previous randomization and overall.

For scientific interpretation, it is important to separate ARIA-H and ARIA-E events and findings in listings and tables.

Using MedDRA standards,

- ARIA-E events is mapped to the following PTs:
“AMYLOID RELATED IMAGING ABNORMALITY-OEDEMA/EFFUSION” or
“VASOGENIC CEREBRAL OEDEMA”
- ARIA-H events is mapped to the following PTs:
“CEREBELLAR MICROHAEMORRHAGE” or “CEREBRAL HAEMOSIDERIN DEPOSITION” or “CEREBRAL MICROHAEMORRHAGE” or “AMYLOID RELATED IMAGING ABNORMALITY-MICROHAEMORRHAGES AND HAEMOSIDERIN DEPOSITS.”

AESIs are discussed in more detail in the study protocol Section 5.2.3. AESIs in this study will be captured by recording all case details on the AE eCRF.

In the tables of study drug related AEs or SAEs, if a patient has more than one occurrence of an event, the most closely related event will be counted. If the relationship of an AE to the study drug is missing, then the AE will be included only in the total number of events column, but not in the count of patients with the related event.

The AE and SAEs incidence rates per patient-years in the OLE will be calculated as the total number of occurrences divided by the total duration of treatment in the OLE in patient-years for each specified population or group. The duration of treatment in the OLE is from the start of OLE until 4 weeks after last dose in the OLE.

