3.4.2.1 Rationale for Duration of Study Follow-Up (16 Weeks)

The primary purpose for the 16-week follow-up visit (i.e., 16 weeks after the last dose) is to evaluate the residual effects of gantenerumab. The apparent terminal half-life of gantenerumab is in the order of 24 days and gantenerumab is cleared from plasma after approximately 17 weeks (approximately 5 half-lives). Therefore, safety assessments performed 16 weeks after the last dose are considered sufficient to evaluate residual effects on peripheral safety outcomes. In addition, efficacy assessments at the follow-up visit may support the enduring effect of gantenerumab after treatment is stopped. *The follow-up visit at 16 weeks is not required for patients who enroll in Study WN41874 (open-label rollover study).*

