5.3.1 Adverse Event Reporting Period

Investigators or their designees will seek information on adverse events at each patient contact. All adverse events, whether reported by the patient or noted by study personnel, will be recorded in the patient's medical record and on the Adverse Event eCRF.

After informed consent has been obtained **but prior to initiation of study drug**, only serious adverse events caused by a protocol-mandated intervention (e.g., invasive procedures such as biopsies, discontinuation of medications) should be reported (see Section 5.4.2 for instructions for reporting serious adverse events).

After initiation of study drug, all adverse events, regardless of relationship to study drug, will be reported until 52 weeks after the last dose of *study drug during Part 1 and until 4 or 16 weeks, as applicable, after the last dose of study drug during Part 2*. After this period, the investigator should report any serious adverse events that are believed to be related to study drug treatment (see Section 5.6).

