4.1.5 Safety Follow-Up Population

The safety follow-up population will include all patients who did not enter the OLE who had a vital signs visit date, AE start date or study completion or discontinuation date greater than 28 days after their last intake of study-drug in double-blind. It will also include all patients who entered the OLE whose first dose in the OLE was greater than 28 days after their last dose in double-blind. The time each patient spent in follow-up is also defined by these dates.

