Patients received open-label gantenerumab for an initial 2 years treatment and up to an additional 3 years beyond the initial 2 years of OLE (5 years of OLE in total), followed by a safety and limited efficacy assessment 4 weeks after the last dose. Patients in the OLE were given the option to continue receiving open-label gantenerumab treatment until the end of 2020. The first dose of open-label gantenerumab was administered after the patient had signed the OLE informed consent form.

At the end of the study, patients were given the option of enrolling in the open-label rollover study (WN41874), aimed at evaluating the safety and tolerability of long-term administration of doses up to 1200 mg of gantenerumab. Patients who did not enroll in Study WN41874 had one additional follow-up visit at 16 weeks after the final dose for safety and limited efficacy assessments.

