4. ANALYSIS POPULATIONS

All Enrolled Population

All enrolled population includes all patients that were enrolled in the OLE.

Safety Evaluable Population

The safety-evaluable (SE) population includes patients who received of at least one dose of gantenerumab during the OLE. Analysis using this population will be performed by previous randomization, which is the treatment assignment in the DB part, and overall or by actually received up-titration scheme (as needed), and overall.

Safety Population with Post Open-Label Extension Baseline Magnetic Resonance Imaging

The safety population with post-OLE baseline MRI includes patients in the SE population who had at least one post-OLE baseline MRI.

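### The OLE follow-up adverse event table defaults to all treated patients as its denominator, so any percentage in it is diluted by patients who have no follow-up time

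*SAP*

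**What the plan says.** **OLE SAP**

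- Section 5.7.2 separates a treatment period, ending 4 weeks after the final OLE dose, from a follow-up period: "AEs during the follow-up period (from 4 weeks after the last dose in the OLE until the CCOD) will be summarized and listed". The display is by previous randomization and overall. No population is named for it.
- Section 5.7 sets the default for every safety display: "Descriptive statistics will be used to analyze all safety data in the SE population, unless otherwise specified".
- Section 4 defines that set: "The safety-evaluable (SE) population includes patients who received of at least one dose of gantenerumab during the OLE". The other two sets in section 4 are all enrolled patients and SE patients with a post-baseline MRI. Neither is conditioned on follow-up.
- On the statistic, section 5.7.2 says "the frequency of each AE preferred term (PT) will be defined as the number of patients experiencing at least one occurrence of the event", and it sorts tables by overall incidence. Its patient-year rates divide by treatment duration, which stops 4 weeks after the last dose.
- Section 1.2 says who is seen later: "Patients who did not enroll in Study WN41874 had one additional follow-up visit at 16 weeks after the final dose".

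**Protocol**

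- Section 5.3.1 has all AEs reported "until 4 or 16 weeks, as applicable, after the last dose of study drug during Part 2".
- Section 3.4.2.1 says the primary purpose of the 16-week visit "is to evaluate the residual effects of gantenerumab", and waives that visit for WN41874 enrollees.

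**Part 1 SAP**

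- Section 4.1.5 defines a safety follow-up population. It consists of patients outside the OLE with a vital signs visit, AE start, or completion or discontinuation date "greater than 28 days after their last intake of study-drug in double-blind", plus OLE entrants whose gap between the two phases exceeded 28 days. It also defines each patient's time in follow-up.

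**The concern.** An incidence needs a denominator of patients who were observed during the period in question. Here the default denominator includes a group for whom routine collection stops at about the moment the period begins. These patients count in full below the line and add almost nothing above it.

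The 16-week visit exists to look for residual effects, and the main objective of the extension is safety and tolerability. A post-treatment percentage that is too low gives false reassurance on the question the visit was meant to answer. The reader of the table cannot correct it, because neither the number followed nor the time followed would be shown beside it.

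**Working it through.** The plan states no figure for this table, so there is nothing to reproduce. The check traces the denominator and then does simple arithmetic.

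**Step 1: which denominator applies.** OLE SAP 5.7.2 names none, section 5.7 supplies SE, and section 4 makes SE everyone dosed in the OLE. OLE SAP section 1 reports 230 OLE entrants, so N is at most 230. The Protocol gives 299 (synopsis) and 229 (section 3.1.2) as the number invited. N cancels below, so the choice does not matter.

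**Step 2: who has observation time in the window.** The window opens at week 4 after the last dose.

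- Not enrolled in WN41874: routine AE reporting runs to week 16, so up to 12 weeks are observed.
- Enrolled in WN41874: the last visit is Follow-Up 1 at week 4 and routine reporting ends there. The ±7-day visit window can add at most a few days.
- Died before week 4, or withdrew consent before week 4 (Protocol 4.7.1 and 4.7.2.1 stop all follow-up at withdrawal of consent): none.

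**Step 3: the dilution.** Let s be the share of SE patients with no follow-up time and p the incidence among those followed. The number followed is N(1 − s) and the number with an event is pN(1 − s). Dividing by N:

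reported percentage = p × (1 − s)

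The share s is not in the documents and is assumed here. For p = 10%:

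| Assumed s | Calculation | Reported |
|---|---|---|
| 10% | 10% × 0.90 | 9.0% |
| 25% | 10% × 0.75 | 7.5% |
| 50% | 10% × 0.50 | 5.0% |
| 75% | 10% × 0.25 | 2.5% |
| 90% | 10% × 0.10 | 1.0% |

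If a fraction q of the unfollowed patients still has an event recorded, the reported figure is p(1 − s) + qs. This stays below p whenever q is below p.

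**Step 4: whether another display compensates.** The patient-year rate does not, since its person-time ends where this window starts. For scale, if all 230 patients were followed for 12 weeks (84 days), follow-up would total 230 × 84 / 365.25 = 52.9 patient-years. At s = 50% it is 26.4. Neither figure appears in any planned output.

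**Step 5: after the change.** With only the followed patients in the denominator, the reported percentage is p at every value of s.

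**The case against.** The strongest reply is that the SAP never prints a percentage for this table. It defines frequency as a count of patients, promises listings, and leaves output layouts out of scope. Counts and listings are not diluted, the extension has no hypotheses, and the main AE tables and rates cover the treatment period. All of that stands, and it limits the point to one descriptive table. It does not remove the point: the same section orders its tables by incidence, and the only stated rule for the denominator is the SE default.

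A reader might be tempted by three stronger readings that the documents do not support.

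- *Rollover patients cannot have an AE in this period.* Protocol 5.3.1 and 5.6 keep serious events believed related to study drug reportable after the routine period, the SAP window runs on to the clinical cutoff date, and a late Follow-Up 1 can fall after day 28. Routine capture stops, but capture is not impossible.
- *Part 1 solved this and the OLE SAP dropped the solution.* Part 1 SAP 4.1.5 defines a suitable population, but its safety sections do not explicitly assign that population to an AE table. It is a precedent for the definition only.
- *The comparison between previous-randomization columns is distorted.* That needs unequal shares. At 40% and 60%, equal incidences of 10% would read 6% and 4%, but nothing in the documents suggests the shares differ, and no test between the columns is planned.

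Rollover is also offered only to patients still on treatment at study end (Protocol 4.3.4). Those who stop earlier are asked to attend both follow-up visits, so the unfollowed share could be modest.

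**Conclusion.** The point holds as a denominator defect in one safety table. Under the stated default, any percentage or incidence of follow-up AEs is too low by the factor (1 − share with no follow-up). The direction is downward whenever that share is above zero and unfollowed patients have fewer recorded events than followed ones, which the reporting rules make close to certain. The size is unknown because the documents do not give the number who rolled over; 7.5% or 5% in place of 10% rests on assumed shares of 25% and 50%. The conclusion also rests on reading the section 5.7 default as governing this table, since 5.7.2 does not restate it. The treatment-period AE tables, the patient-year rates, the raw counts and the listings are not affected.

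**What to change.** In OLE SAP section 4, add an OLE safety follow-up population: SE patients with observed study time more than 28 days after their last OLE dose. Base this on a visit, study completion or study discontinuation date. Do not let the occurrence of an AE alone admit a patient, as the AE-start criterion in Part 1 SAP 4.1.5 does, because the outcome would then select its own denominator.

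End each patient's follow-up time at the earliest of study completion or discontinuation, first WN41874 dose where available, and the clinical cutoff date. Do not exclude WN41874 enrollees outright: one with a real off-drug gap contributes genuine post-treatment time, and Part 1 SAP 4.1.5 likewise keeps patients whose gap before the next phase exceeded 28 days.

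In section 5.7.2, name this population as the denominator for the follow-up AE table, and show follow-up patient-years by previous randomization and overall. Patient-years also handle rollover patients who enter with only a few days because Follow-Up 1 fell late in its window.

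The cost is one extra population definition and one denominator. The documents do not say whether first-dose dates from WN41874 are held in this study's database, hence the qualifier above. The table will rest on a smaller, selected group, mostly patients who did not roll over, and a footnote should say so.

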- An adverse event will be included in the summary table of adverse events leading to study drug discontinuation if the “action taken with blinded gantenerumab” drop-down menu on the Adverse Event CRF is checked “drug withdrawn”.
- In the summary table of adverse events by intensity, if a patient has more than one occurrence of an event, the event with the most severe intensity will be counted. If the intensity of an adverse event is missing, then the adverse event will be included only in the total number of events column, and not in the count of patients with the event by intensity.

For scientific interpretation it is important to separate ARIA-H and ARIA-E events in listing and tables. However, using MedDRA standards, both get mapped to the preferred term 'AMYLOID RELATED IMAGING ABNORMALITIES'. Furthermore, there are some additional terms that the Clinical Science and Safety Science teams deem to be ARIA-E or ARIA-H that have separate MedDRA preferred terms. To overcome this, baskets will be implemented to summarize all ARIA-H events together and all ARIA-E events together. These baskets are defined below:

- ARIA-E
 - Preferred term: 'VASOGENIC CEREBRAL OEDEMA' or
 - Lower level terms: 'AMYLOID RELATED IMAGING ABNORMALITY-OEDEMA/EFFUSION' or 'AMYLOID RELATED IMAGING ABNORMALITY-OEDEMA/EFFUSION' or 'ARIA-E'
- ARIA-H

- Preferred term: 'CEREBELLAR MICROHAEMORRHAGE' or 'CEREBRAL HAEMOSIDERIN DEPOSITION' or 'CEREBRAL MICROHAEMORRHAGE'
- Lower level terms: 'AMYLOID RELATED IMAGING ABNORMALITY-MICROHAEMORRHAGE AND HAEMOSIDERIN DEPOSITS' or 'AMYLOID RELATED IMAGING ABNORMALITY-MICROHEMORRHAGES AND HEMOSIDERIN DEPOSITS' or 'ARIA-H'

Instances where an AE has MedDRA preferred term 'AMYLOID RELATED IMAGING ABNORMALITIES' but does not fit into one of the two baskets above, will be assessed on a case-by-case basis.

In the summary table of adverse events by relationship to study drug, if a patient has more than one occurrence of an event, the most closely related event will be counted. If the relationship of an adverse event is missing, then the adverse event will be included only in the total number of events column, and not in the count of patients with the event by relationship.

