5.7.2.2 CNS Symptoms Temporally Associated with ARIA-E MRI Findings

In this report, symptomatic ARIA-E is defined as onset or worsening of CNS symptom(s) that is/are temporally associated with ARIA-E MRI findings. A programmatic approach to capture symptomatic ARIA-E will be adopted in the analysis, since CNS symptoms have not been consistently captured in the CRF AE form. For programmatic retrieval, CNS symptoms temporally associated with ARIA-E MRI findings were defined as all AEs from the Nervous System Disorders and Psychiatric Disorders SOCs that had onset between 4 weeks prior to ARIA-E onset through ARIA-E resolution, and not falling under ARIA-associated PTs.

The list of ARIA-associated PTs include:

- Amyloid related imaging abnormalities
- Amyloid related imaging abnormality-microhaemorrhages and haemosiderin deposits
- Amyloid related imaging abnormality-oedema/effusion
- Cerebral amyloid angiopathy
- Brain oedema
- Vasogenic cerebral oedema
- Brain stem microhaemorrhage
- Cerebellar microhaemorrhage
- Cerebral microhaemorrhage
- Cerebral haemosiderin deposition
- Magnetic resonance imaging head abnormal
- Superficial siderosis of central nervous system

The CNS symptoms temporally associated with ARIA-E MRI findings (programmatic retrieval) will be listed and summarized by previous randomization and APOE ϵ 4 genotype, and overall. A listing of AE reported as Symptoms of ARIA-E (eCRF) will be provided as well.

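### The OLE grouping of ARIA-H adverse events omits two preferred terms that the same SAP lists as ARIA-associated, and no rule covers the unspecific ARIA term

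*SAP*

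**What the plan says.** The SAP document holds two plans, one for Part 1 and one for the OLE.

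**OLE SAP, section 5.7.2 (Adverse Events).** The plan says that "it is important to separate ARIA-H and ARIA-E events and findings in listings and tables". It then fixes two groups. The first ("ARIA-E events is mapped to the following PTs") has two PTs and the second ("ARIA-H events is mapped to the following PTs") has four.

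**OLE SAP, section 5.7.2.2 (CNS symptoms associated with ARIA-E).** CNS symptoms are retrieved by program as nervous-system and psychiatric AEs in a time window around ARIA-E, "and not falling under ARIA-associated PTs". The sentence opening "The list of ARIA-associated PTs include" introduces twelve PTs, among them "Brain stem microhaemorrhage" and "Superficial siderosis of central nervous system".

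**Part 1 SAP, section 4.5.2 (Adverse Events).** Here "baskets will be implemented to summarize all ARIA-H events together and all ARIA-E events together". The baskets combine PTs with lower-level terms, because MedDRA then mapped both kinds of ARIA to one PT. Events with that unspecific PT that fit neither basket are reviewed one by one.

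**OLE SAP, section 5.7.3 (MRI safety findings).** ARIA-E and ARIA-H incidence and severity are summarized separately, in patients with at least one MRI after OLE baseline.

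**The concern.** One plan holds two ARIA term lists that differ, and gives no reason. A PT on the longer list but in neither group is treated as ARIA when it is removed from the symptom search, yet not when ARIA AEs are grouped.

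Safety and tolerability at higher doses is the OLE's primary objective (OLE SAP 1.1.1), and ARIA is an identified risk (protocol 5.1). MRI reads can give incidence and severity. Seriousness, investigator-assessed relatedness, discontinuation and dose interruption are specified as AE summaries in OLE SAP 5.7.2. A reader who wants those attributes for ARIA-H as a whole will look to the grouped AE result. The table of adverse events of special interest does not fill the gap, because protocol 5.2.3 limits that category to potential drug-induced liver injury and suspected transmission of an infectious agent. A missing term can only lower a grouped count or leave it unchanged, so any error is in the reassuring direction.

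**Working it through.** The plan states no figure to reproduce. The check compares the two lists.

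| PT listed in OLE SAP 5.7.2.2 | Group in OLE SAP 5.7.2 |
|---|---|
| Amyloid related imaging abnormality-oedema/effusion | ARIA-E |
| Vasogenic cerebral oedema | ARIA-E |
| Amyloid related imaging abnormality-microhaemorrhages and haemosiderin deposits | ARIA-H |
| Cerebral microhaemorrhage | ARIA-H |
| Cerebellar microhaemorrhage | ARIA-H |
| Cerebral haemosiderin deposition | ARIA-H |
| Brain stem microhaemorrhage | none |
| Superficial siderosis of central nervous system | none |
| Amyloid related imaging abnormalities (unspecific) | none |
| Brain oedema | none |
| Cerebral amyloid angiopathy | none |
| Magnetic resonance imaging head abnormal | none |

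1. **Count.** The groups hold 2 + 4 = 6 PTs. All 6 are on the twelve-term list, so 12 − 6 = 6 PTs are in neither group.

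2. **Which of the six belong in ARIA-H on the trial's own terms?** Protocol 5.2.4 describes ARIA-H as findings suggesting microhemorrhages and hemosiderin deposits, with no limit on location. The group already has the cerebral and cerebellar microhaemorrhage terms, and the brain stem term differs from them only in site. Protocol 4.1.2.2 counts microbleeds and areas of leptomeningeal hemosiderosis together for eligibility, and Part 1 SAP section 2 spells out ARIA-H as microbleed/hemosiderosis. I read superficial siderosis as the coded counterpart of that hemosiderosis. On this reading two PTs belong in the group and are missing from it.

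3. **The unspecific ARIA PT.** The Part 1 SAP has two devices for it: lower-level terms, then individual review of what remains. The OLE SAP has neither. It lists separate PTs for ARIA-E and ARIA-H (MedDRA 24.0, against Version 20 in Part 1), so most reports should now separate at PT level. A report still coded to the unspecific PT has no route into either group.

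4. **The Part 1 baskets.** The ARIA-H basket names three PTs (cerebellar microhaemorrhage, cerebral haemosiderin deposition, cerebral microhaemorrhage) plus ARIA-H lower-level terms. The same two PTs are absent, and the individual review covers only the unspecific PT.

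5. **Size.** No counts by PT are given, so the effect cannot be computed. A patient count falls only for a patient with no other event in the group. If all 230 patients who entered the OLE (OLE SAP 1) received a dose, each such patient lowers the overall grouped percentage by 1/230 = 0.43 percentage points. The number of such patients is unknown and may be zero.

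**The case against.** The twelve-term list is not a definition of ARIA. It is an exclusion list that keeps imaging findings from being counted as symptoms, and it is broad on purpose: it includes an abnormal head MRI and cerebral amyloid angiopathy. A broad exclusion list and a narrower event definition can properly differ. This stands. A reader might infer that all six ungrouped PTs should be added, or that brain oedema should be moved to ARIA-E. The documents do not support that: brain oedema is not specific to ARIA, and leaving it out is defensible. The case for the two ARIA-H terms rests instead on the protocol's description of ARIA-H and on the terms already in the group.

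Nothing disappears from the report. OLE SAP 5.7.2 tabulates every AE under its own PT, so an ungrouped event still appears in the serious, related, discontinuation and interruption tables that apply to it. This also stands, and it confines the problem to grouped results. Nor does the exclusion from the symptom search do harm in itself, since an imaging finding is not a symptom.

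The main ARIA estimate comes from MRI. Scans are read centrally (OLE SAP 1.2.2), and section 5.7.3 does not say that it uses the AE groups. This stands too.

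The separate ARIA-E and ARIA-H PTs in the OLE SAP largely remove the need for a split by lower-level term. I agree. Only a rule for the remaining unspecific reports is missing.

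Finally, the Part 1 SAP has no longer list for its baskets to contradict. That is so; the reason to change Part 1 is consistency between the two reports.

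**Conclusion.** The concern holds in a limited form. Followed as written, OLE SAP 5.7.2 would leave events coded to brain stem microhaemorrhage or superficial siderosis of central nervous system out of the ARIA-H group, and events with the unspecific ARIA PT out of both groups. Grouped ARIA AE counts can therefore be understated.

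A reader might go further and conclude that ARIA was undercounted in the AE tables, or put a figure of several percentage points on it. The documents show neither. The effect is zero if no event was coded to these terms, and any assumed number of affected patients would be a guess.

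The conclusion assumes that superficial siderosis corresponds to the hemosiderosis that the protocol counts with microbleeds, and that the groups in 5.7.2 will be used to report ARIA AEs. The SAP does not name the tables that will use them. This is a gap in a definition, worth closing because it is cheap and concerns an identified risk.

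**What to change.** 1. In OLE SAP 5.7.2, add brain stem microhaemorrhage and superficial siderosis of central nervous system to the ARIA-H group, or state why they are left out.
2. Add to the OLE SAP the Part 1 rule that events with the unspecific ARIA PT that fit neither group are reviewed case by case, and report how each was assigned.
3. Add the same two PTs to the Part 1 ARIA-H basket, where the dictionary version used there has them, so that the two reports group alike.
4. Say in 5.7.2 that the list in 5.7.2.2 is an exclusion list and is meant to be broader than the groups.

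The cost is an edit to the term lists in the SAPs and programs, plus review of any unspecific reports. No new data are needed. A count of AEs coded to the three PTs would show at once whether any result changes.

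### Adverse events with missing causality (in Part 1 also missing intensity) are left out of the patient counts, so within a group the related and severe counts can be too low but never too high

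*SAP*

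**What the plan says.** The OLE SAP, Section 5.7.2, sets the rule for the tables of drug-related AEs and SAEs. On an AE with no causality entry it states: "If the relationship of an AE to the study drug is missing, then the AE will be included only in the total number". The place meant is the column that totals events; the patient column of the same table leaves the AE out. Just before this it says that for a patient with repeated occurrences "the most closely related event will be counted".

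The Part 1 SAP, Section 4.5.2, has the matching rule for its table by relationship: "If the relationship of an adverse event is missing, then the adverse event will be included only in the total number of events column". Patients are not counted on the strength of such an AE. The table by intensity is treated the same way: "If the intensity of an adverse event is missing, then the adverse event will be included only in the total number of events column". Here too the patient column omits it. When a patient has repeated occurrences, that table takes the worst recorded one: "the event with the most severe intensity will be counted".

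Both SAPs define the frequency of a preferred term as a number of patients. In Part 1 that number is also the numerator of the incidence rate per patient-year. The OLE rates use numbers of occurrences instead. The OLE SAP has no rule for missing intensity. Neither SAP plans a missing category or a sensitivity count for these fields.

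**The concern.** The patient count is the figure that readers take from a safety table, and here a blank can only remove a patient from the related or severe count. For repeated occurrences the same sections choose the worst recorded one, so the handling of blanks runs the other way, and no reason is given.

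Safety and tolerability is the main objective of the OLE. In Part 1 the protocol (Section 6.1.7) withdrew the primary and key secondary efficacy analyses, although the Part 1 SAP still fits a repeated-measures model to the two co-primary scales. Related SAEs are likely to be few, so one blank can be a visible share of the count.

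The OLE wording raises a second issue. A blank-causality AE goes into the events column of a table of related AEs, while its patient stays out of the patient column. The two columns then rest on different definitions of related.

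**Working it through.** The plan gives no figure to reproduce: no missing rate and no related-AE count. The check is of direction first, then of size under stated assumptions.

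**Direction, causality.** Take one patient with k occurrences of a preferred term (k = 1, 2, 3). Each occurrence is truly related or not, and its causality is recorded or blank, which gives 4^k configurations: 4 + 16 + 64 = 84.
- Patient count too low: at least one related occurrence, all of them blank. Number = 3^k − 2^k, so 1 + 5 + 19 = 25.
- Patient count too high: 0, because a patient is counted only on a recorded related occurrence.
- OLE events column, read literally (blanks included): too high whenever an unrelated occurrence is blank. Number = 4^k − 3^k, so 1 + 7 + 37 = 45. Too low: 0.

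**Direction, intensity (Part 1).** With three intensities, recorded or blank, there are 6^k configurations: 6 + 36 + 216 = 258.
- Severe patient count too low: 5^k − 4^k, so 1 + 9 + 61 = 71. Too high: 0.
- In 60 of the 258 the patient is shown as mild or moderate when the worst occurrence was of higher intensity.

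These configurations are not equally likely. The counts show direction only.

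**Size.** Inputs: 230 patients entered the OLE (OLE SAP, Section 1). Assumed: one AE per patient, true related share p, and missing fraction m independent of causality. Shortfall in patients = 230 × p × m.
- m = 0: none.
- m = 1%: 230 × 0.10 × 0.01 = 0.23 to 230 × 0.50 × 0.01 = 1.15.
- m = 10%, p = 50%: 230 × 0.50 × 0.10 = 11.5, or 5.0 percentage points.

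For a rare category, one blank among five truly related SAEs is 1/5 = 20%, provided that patient has no other recorded related occurrence of the event.

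**Blanks counted as related instead.** Count = 230 × [p(1 − m) + m]. With p = 30% the true count is 69.

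| m | SAP rule | Blanks as related |
|---|---|---|
| 1% | 68.31 (−0.69) | 70.61 (+1.61) |
| 5% | 65.55 (−3.45) | 77.05 (+8.05) |
| 10% | 62.10 (−6.90) | 85.10 (+16.10) |

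The true count lies between the two columns.

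**Between arms in Part 1.** Assume true related rates of 25% on gantenerumab and 10% on placebo, a difference of 15.0 points.
- 5% blank on placebo only: 25 − 10 × 0.95 = 15.5.
- 5% blank on gantenerumab only: 25 × 0.95 − 10 = 13.75.
- 5% blank in both: 23.75 − 9.5 = 14.25.

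**The case against.** The strongest reply is that little is lost. The protocol requires severity and causality for every AE (Section 5.3), records causality as yes or no (Section 5.3.4), has discrepant data queried (Section 7.1) and requires SAEs to be reported within 24 hours (Section 5.4). Blanks should be few. Safety is descriptive, and the identified risks, ARIA and injection-site reactions, are summarised without regard to investigator causality. Counting blanks as related can also be further from the truth than the present rule, as the table shows. All of this stands. It limits the size and argues against imputation alone, but not against showing the blanks.

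A reader might also infer more than the documents support:
- *That the events are dropped.* They stay in the event totals and in the all-AE and all-SAE tables. Only the sub-classification is affected.
- *That unknown is recoded as unrelated or mild.* In Part 1 such an AE enters no category at all; it is unclassified.
- *That the arm comparison is tilted towards the drug.* The one-way direction holds within a group. The difference can move either way.
- *That both SAPs are otherwise conservative.* Part 1 does place AEs with no dates after first dose, but the OLE SAP has no such AE rule, and Part 1 sets missing NPI sub-scores to 0 (Section 2.3.2.3).
- *That blanks cluster around withdrawal or death.* Nothing in the documents says so.

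**Conclusion.** The point holds as a minor one. Within a group, the related patient counts in both parts and the severe patient count in Part 1 are understated or unchanged, never overstated. In Part 1 any shortfall carries into the incidence rates; the OLE rates, built on occurrences, are not affected by this route. A patient with another recorded related or severe occurrence of the same event is still counted.

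The size cannot be derived from the documents. A missing rate of 0 to 1% is an assumption, based on the protocol's requirement to assess every AE. With 10% to 50% of patients having a related AE, also assumed, it means a shortfall of at most about one OLE patient in 230. The mismatch between the OLE columns is one of definition and needs clarifying whatever the number of blanks.

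**What to change.** In both SAPs, replace the rule with three provisions:
1. Show patients and events with missing relationship, and in Part 1 missing intensity, as a separate missing category by group: treatment arm in Part 1, previous randomization and overall in the OLE.
2. Give the related AE and related SAE patient counts with missing relationship counted as related. State in a footnote how many patients are counted only for that reason. Subtracting that number returns the count from recorded causality, so the reader sees both bounds.
3. Use the same set of events in the events column and the patient column of each related-AE table.

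For intensity, the missing category is enough; blanks need not be counted as severe.

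The cost is a short paragraph in each SAP, one extra table category and a footnote. If there are no blanks, no count changes. The downside is that related counts may rise slightly and can overstate, which the footnote makes visible.
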